5.9 Subgroup Analyses

Relevant efficacy and safety summaries will be repeated for the following subgroups, using the primary analysis population:

- Age (completed years): < 18, 18 – 30, 31 – 35
- Parity: nulliparous vs. parous
- Race: White vs. Non-white
- Body Mass Index (BMI; kg/m² round to one decimal place): ≤ 24.9 , 25.0 – 29.9, 30.0 – 39.9, ≥ 40
- LNG20 inserter: original (protocol versions 1.0-4.0) vs. redesigned (protocol versions 5.0, 6.0, 7.0, 8.0, 9.0)

The Pearl Index will not be calculated within each of these subgroups; instead, crude efficacy rates will be presented. The Pearl Index calculation becomes less meaningful and difficult to interpret in this situation as the number of available cycles for the exposure denominator necessarily and rapidly diminishes. Also, because these calculated rates rely on the number of subjects as the denominator, individual 28-day cycles of use where other contraceptive methods have been reported will not be considered for exclusion.

6. ANALYSIS POPULATIONS

The Safety population will include all subjects enrolled who underwent the IUS insertion procedure, regardless of age and outcome. Treatment assignment will be based on the treatment actually received.

The following subject populations will be used for efficacy analyses:

- Modified Intent-to-Treat (MITT) population will include all subjects between 16 and 35 years of age at study entry for whom the assigned IUS is successfully

placed in the uterus and for whom there is at least one assessment of pregnancy status after inserting the IUS.

- Per-Protocol (PP) population will include subjects in the MITT population with no major protocol deviations (to be identified prior to database cut-off).

The Treatment Pharmacokinetics (PK) population will include all subjects enrolled in the substudy and have at least one post-insertion PK assessment and no major protocol deviations.

The Elimination PK population will include all subjects enrolled in the substudy (who will be randomized to one time point post-IUS removal) and whose post-IUS removal PK assessment is not missing. The elimination PK sampling will only be obtained at the full intended duration of use IUS removal visit (i.e. Month 121).

The Endometrial Thickness (ET) population will include all subjects enrolled in the ET substudy and have at least one post-insertion ET measurement. The final endometrial thickness measurements will be obtained at baseline, Month 12, Month 60 and after the full intended duration of use (i.e. 10 years).

7. STUDY POPULATION SUMMARIES

7.1 Subject Disposition

Subject disposition information will be summarized for all subjects, by treatment group and by site. Summaries will include: the number of enrolled subjects, the number of subjects with successful IUS insertion (first and second attempt), the number of subjects who discontinued after failed insertion, the number of subjects in each analysis population, the number of subjects completing each visit and the study, and the primary reason for discontinuation.

7.2 Protocol Deviations

Major protocol deviations that could potentially affect the primary protocol outcome (efficacy) will be identified prior to database cut-off.

7.3 Demographic and Baseline Characteristics

Demographic variables include: age, sex, ethnicity, and race. Other baseline characteristics include: marital status, partner status, height, weight, BMI, medical history, gynecological history, menstrual history, and pregnancy history. General

menstrual history, menstrual history on hormones in the last three months and without hormones in the last three months will be summarized.

Demographic and baseline characteristics will be summarized for the Safety, MITT, Treatment PK, Elimination PK, and ET populations. If the MITT and PP populations are not equivalent, the demographic and baseline characteristics will be summarized for the PP population as well.

8. TREATMENT AND MEDICATION

8.1 Pre-trial and Concomitant Medications

Verbatim terms on eCRFs will be mapped to the narrowest Anatomical/Therapeutic/Chemical (ATC) class possible and generic drug names using the World Health Organization (WHO) Drug Dictionary Enhanced (DDE). For example, if the 4th level is not available, then the 3rd level (pharmacological subgroup) will be provided.

Concomitant medications include any medication or health product (any prescription medications or over-the-counter preparations) taken during the active study treatment period. Pre-trial medications include any medications taken within seven days (30 days for anticoagulants) of enrollment. Concomitant medications will be summarized for each treatment group by WHO ATC class and generic drug name. These summaries will present the number and percentage of subjects using each medication. Subjects may have more than one medication per ATC class and Generic Drug Name. At each level of subject summarization, a subject is counted once if she reported one or more medications at that level. Each summary will be ordered by descending order of incidence of ATC class and generic drug name within each ATC class.

8.2 Extent of Exposure

The number of women-months (28-day cycles) and women-years of exposure will be summarized by treatment group. Exposure to study IUS will be summarized using treatment duration in months both by treatment group and combined across LNG20 treatment groups (16-35 y.o. and 36-45 y.o.).

9. EFFICACY ANALYSES

The primary efficacy analysis will be based on the MITT population. Additional supportive efficacy analyses will be performed using the PP population, unless the populations are equivalent, as well as the Safety Population.

9.1 Pregnancy on Study

For all pregnancy analyses, pregnancy is defined as occurring when a positive urine or blood pregnancy test is reported. Confirmation of pregnancy should be attempted by the study site and may include:

- urine pregnancy test at the study site
- serum quantitative hCG (at study site or report)
- ultrasound examination confirming a pregnancy (at study site or report)
- a surgical procedure for treatment of an extrauterine pregnancy or intrauterine pregnancy (report)

A pregnancy is considered to have occurred "on treatment" if a test or examination confirms a pregnancy and with a date of conception while the IUS is being used as a method of contraception by the subject up to and including 7 days after IUS discontinuation. Pregnancies solely reported by the subject that cannot be verified by any means of examination or follow-up reporting will be evaluated for determination of whether they should be classified as "on treatment" or "not on treatment" for the MITT and PP efficacy evaluations. All reported pregnancies, even if not confirmed by the site, will have a Pregnancy Narrative completed by the study investigator.

9.2 Primary Efficacy Variable

The primary efficacy variable is the Pearl Index, an estimation of the number of unintended pregnancies per 100 women-years of exposure. The Pearl Index is calculated as the number of "on treatment" pregnancies in the study divided by the total number of complete 28-day cycles of use (as defined in Section 5.5) in the study across all participating subjects, that result multiplied by 1300 (13 cycles x 100 years). In the case of subjects who are still on study at the time of a Pearl Index calculation, the last known date of product use (defined in Section 5.4) will be used in place of the IUS discontinuation date. A "last cycle" computed using this algorithm will be considered complete if it is at least 23 days in length. In addition, subjects who become pregnant will have that last cycle counted as completed for the Pearl Index calculation, regardless of length.

For the primary Pearl Index outcome using exposure information through Year 5, the MITT population will be used as the basis of exposure and all 28-day cycles where use of another birth control method was reported in the daily diary will be excluded from the total cycle count denominator. Diary days when no information regarding the use other birth control methods is reported will be considered days when no other birth control method use took place. The Pearl Index will be calculated using both the cumulative data

through Year 10 and as individual, non-cumulative year-by-year estimates (see Section 10.1).

For the definitive assessment of contraceptive efficacy, the Pearl Index and its 95% confidence interval will be considered the primary result for inferences.

9.3 Secondary Efficacy Variables

In addition to the primary Pearl Index efficacy analysis in the MITT population, the Pearl Index will also be calculated as secondary efficacy variables as follows:

- MITT with no cycle exclusions
This calculation will include all “on treatment” pregnancies in the numerator and all cycles of use in the denominator. No cycles will be excluded from the denominator.
- The PP study population: The MITT with no cycle exclusions but excluding those subjects with major protocol deviations. Note that use of other birth control methods, by itself, does not constitute a subject being excluded from the PP population.
- LNG20 subjects 36-45 years old, excluding all 28-day cycles where use of another birth control method was reported in the daily diary. Interpretation of the Pearl Index estimate for this subgroup will require caution since the available number of subjects and 28-day cycles of product use will be small and limiting.
- Safety Population: LNG20 subjects 16-45 years old, excluding all 28-day cycles where use of another birth control method was reported in the daily diary
- Sub-group analysis by parity, BMI and race
- Ectopic pregnancies only

“On treatment” pregnancy rate and its associated 95% confidence interval will also be estimated using life table methods with year of use serving as the principal life-table classification.

Life Table analysis will be conducted on the following populations:

- MITT with cycle exclusions
- MITT with no cycle exclusions
- PP
- LNG20 subjects 36-45 years old with cycle exclusions

- LNG20 subjects 36-45 years old with no cycle exclusions
- Safety Population: LNG20 subjects 16-45 years old
- Sub-group analysis by parity, BMI and race
- Ectopic pregnancies only

The life table evaluation with cycle exclusions adjusts for cycles where another birth control method was used. Specifically, it will incorporate the calculation of an "absolute time"-based duration of use that adjusts for cycles where use of another BCM was reported. Duration of use would be based on the total number of 28-day cycles of exposure adjusted downward to account for those cycles where other BCM use was reported, the result converted into years of product use by multiplying by 28 (number of days per 28-day cycle) and then dividing by 364 (number of days in a 13 28-cycle year).

9.4 Secondary Efficacy Evaluations for Pre-Specified Subgroups

Calculation of crude pregnancy rates, life table evaluation of efficacy and summary of pregnancy outcomes will be performed within each of the subject subgroups defined in Section 5.9 of this SAP. The life table evaluation will include both the unadjusted and cycle-adjusted for other birth control method use algorithms described in Section 9.3. Pearl Index calculations will not be performed within each of these subgroups, per the reasons given in Section 5.9, e.g., the lack of meaningfulness of the Pearl Index when the number of cycles of exposure is reduced as a result of the subgroup breakdown.

10. METHODS OF EFFICACY ANALYSIS

10.1 Primary Efficacy Analyses

The primary efficacy endpoint is the Pearl Index for LNG20 women 16-35 years old. The Pearl Index and associated 95% confidence interval (CI) will be presented using the MITT population to establish efficacy for two years of use. Acceptable precision of the Pearl Index is expected to establish efficacy of LNG20 where acceptable precision is typically defined as the upper bound of the 95% CI being no more than 1 unit greater than the point estimate of the Pearl Index.

Since the number of cycles of exposure during the first year is the lowest, this precision of the Pearl Index may not be fully observable if limited to the first year alone. Therefore, while a Pearl Index estimate at year 1 and its 95% confidence interval will be obtained using the available exposure information for year 1 alone, the upper bound of the

confidence interval associated with that estimate may be wider than the “no greater than 1 unit” criterion for years 2, 3, 4, 5, 6, 7, 8, 9 and 10. The Pearl Index for primary efficacy will therefore be calculated as cumulative and also non-cumulative year-by-year.

10.2 Secondary Efficacy Analyses

10.2.1 Pearl Indices

The cumulative Pearl Index analyses described above for the primary efficacy analysis will also be performed every year after Year 2. The analysis at Years 3, 4, 5, 6, 7, 8, 9 and 10 will only be completed if the efficacy of LNG20 for the preceding years of use meets acceptable precision, where acceptable precision is defined as the upper bound of the 95% confidence interval being no more than 1 unit greater than the point estimate of the Pearl Index. Pearl Index calculations will be done when a minimum of 200 women complete each subsequent year of the study.

10.2.2 Pregnancy Rates

Life table methods will be used to estimate the overall pregnancy rate for each year and the cumulative pregnancy rate after each year. Both uterine and ectopic pregnancies will be included. Pregnancy dating and confirmation will be determined by medical assessments, including ultrasound examination. Confirmed pregnancy is the failure outcome and the corresponding time to pregnancy is the failure time. Time to pregnancy will be calculated as the date of conception minus the date of IUS insertion plus one (partial or completely missing conception dates handled per Section 5.3.5). Subjects who do not get pregnant will be censored at the last pregnancy assessment and failure time will be calculated as the date of the last pregnancy assessment minus the date of IUS insertion plus one.

Additionally, an overall Ectopic Pregnancy (EP) rate will be calculated as EP Rate per 100 Woman Years (WY) for the duration of use:

Number of EPs/WYs (number of 28-day cycles) = $x/100$ WY. The number of 28-day cycles per subject is not to exceed the duration of use being evaluated.

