- Removal of IUS, if not already expelled or removed (at an outside location)
- Retain all removed or expelled IUSs (when possible) per the Study Reference Manual
- Contraceptive counseling
 - Immediate initiation of another method in the office when possible
 - Request to use this method or be abstinent for at least one week to avoid conception within 7 days after IUS discontinuation
- Schedule next appointment

6.7 30-Day Safety Follow-Up

All subjects must have a safety follow-up visit between 30 and 43 days after the Treatment

Completion/Early Discontinuation Visit (except those made lost to follow up or who withdrew consent per section 7.18). If the subject contacts the office with an expulsion that was 30 or more days ago, this visit may be combined with the Early Discontinuation visit.

- Review of adverse events (note: all adverse events occurring within 30 days of IUS discontinuation should be reported on the appropriate adverse event CRF)
- Review of concomitant medications used up to 30 days of IUS discontinuation
- Menstrual history if not using a hormonal method of contraception
- High sensitivity urine pregnancy test (if positive, see Sections 7.4 and 7.5)
- Weight and blood pressure
- Additional contraceptive counseling if needed
- Review with subject that continued telephone or clinic follow-up (as appropriate) is indicated for the following:
 - an ongoing IUS-related adverse event at study discontinuation should be followed monthly until the adverse event resolves or has stabilized
 - any subject electing to use a non-hormonal contraceptive method or no contraception (including those desiring pregnancy) will be followed monthly for up to 3 months after IUS removal/expulsion for return of menses. Any woman who does not menstruate within 3 months following IUS discontinuation will be referred for appropriate evaluation and continue to be followed monthly until menses has occurred or a diagnosis for the cause of the secondary amenorrhea has been established
- Those women desiring a pregnancy after IUS discontinuation will be contacted every three months from their Treatment Completion/Early Discontinuation Visit up to one year to record return to fertility.
 - Once a pregnancy is reported no further follow-up contact is required.
 - Women who do not become pregnant and change their intention before completing a full 12 months of follow-up will be discontinued from the study and not be included in the return to fertility cohort.

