- If, during on-study contact with the subject (e.g., Month 9 Contact, Month 15 Contact, Month 21 Contact), she reports that the IUS is no longer in place, the date of contact minus 1 day or last date at which a pregnancy test was performed (at study site or outside laboratory with copy of report), whichever is later, will be used as the last date associated with IUS use.
- Subjects who become pregnant with the IUS still in place will have their estimated date of conception used as the last IUS use date.
- In the cases of subjects who are lost to follow-up or withdraw consent prior to IUS removal and neither a last contact date nor a last pregnancy test date is available, the IUS insertion date + 1 day will be used as the last date associated with IUS use.

Similarly, for subjects who had a successful IUS insertion but who have not yet had any post-insertion data (e.g., diaries or post-insertion pregnancy test results) retrieved at the site which could be used to directly calculate duration of use, the IUS insertion date +1 day will be used as the last date of IUS use for the purpose of analysis. For the summary of duration of product use, all subjects with ≥ 1 days of product use, as defined in this section, will be included in the calculations. For the evaluation of adverse events, subjects with less than one calculated complete 28-day cycle of use (at least 23 days) will be excluded unless such subjects reported an adverse event at any time during the first 28 days following IUS insertion (see Section 11.2: Adverse Events for more detail).

5.5 28-Day Cycles of Use Calculation for Efficacy Evaluation

In addition to the calculation of 28-day cycles based on last date of IUS use as described in Section 5.4, the efficacy evaluation requires the exclusion of cycles from the Pearl Index denominator where the use of other birth control methods was reported. Since this information is obtained exclusively from subject daily diaries, 28-day cycles of use need to be calculated from the diary data so as to be able to determine when the use of other birth control methods occurred.

Using the same algorithm described in Section 5.4, each recorded diary date between the IUS insertion date and the last calculated date of product use, inclusively, is compared to the IUS insertion date in order to calculate cycle number and day. Duration of use expressed as the number of 28-day cycles is then calculated as the maximum duration

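### Life tables without cycle exclusions keep leavers at risk until a pregnancy test done 30-43 days after the discontinuation visit, and an undated device loss can be dated after it was reported

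*SAP*

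**What the plan says.** **Life table.** SAP 10.2.2 states: "Subjects who do not get pregnant will be censored at the last pregnancy assessment". It gives no cap at removal or expulsion. SAP 9.3 describes the life-table estimate as an on-treatment pregnancy rate, and SAP 9.1 limits on-treatment to conception "while the IUS is being used as a method of contraception by the subject up to and including 7 days after IUS discontinuation".

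**Test after removal.** Protocol 6.7 says: "All subjects must have a safety follow-up visit between 30 and 43 days after the Treatment" Completion/Early Discontinuation Visit, and lists a urine pregnancy test among its procedures. Women lost to follow-up or who withdrew consent are exempt.

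**Undated device loss.** SAP 5.4 covers a woman who reports that the IUS is gone when the date is unknown. The candidates are "the date of contact minus 1 day or last date at which a pregnancy test was performed", and the rule is "whichever is later, will be used as the last date associated with IUS use". SAP 5.3.5 has another rule for a missing expulsion or removal date: it becomes the last clinic visit. A date with only month and year is also moved forward to that visit if it would otherwise fall earlier.

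**Provisions that limit the effect.** Cycles of use end at the recorded removal or expulsion date when there is one (SAP 5.4). The smaller of the Section 5.4 and diary cycle counts is used (SAP 5.5). The cycle-adjusted life table runs on cycle-based duration (SAP 9.3). Pregnancies after an unrecognized expulsion count in the primary analysis (Protocol 9.7).

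**The concern.** A rate needs a numerator and a time at risk that cover the same period. Here the event window closes 7 days after discontinuation, but a non-pregnant woman stays in the risk set until her last test, which for most leavers would be the safety follow-up test. The surplus time can only lower the estimate. It also carries women who leave late in one year of use into the next year's risk set. In the 36-45 group it places women who complete at Month 96 in year 9, when no device use is planned.

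There is a consistency problem too. SAP 9.3 sets MITT with cycle exclusions beside MITT without them. If the two end exposure by different rules, the comparison mixes the effect of other contraception with a change in censoring.

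For undated losses, the later-of-two rule lets a test done after the woman has reported the IUS gone count as IUS use. This reaches the primary Pearl Index denominator.

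**Working it through.** No figure in the documents is derived from these rules, so there is nothing to reproduce. The check is of the text, followed by a sizing.

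**1. Days without a countable event.** The test falls 30-43 days after the discontinuation visit, and the first 7 days remain in the event window: 30 - 7 = 23 and 43 - 7 = 36. This assumes the device comes out at that visit.

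**2. Inputs (Protocol 9.1, SAP 4).** 1,600 women; annual discontinuation of 20%, 19%, 17%, then 16% in each of years 4-10; planning Pearl Index 0.280.

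**3. Women remaining at each year end.** 1,280; 1,036.8; 860.5; 722.9; 607.2; 510.0; 428.4; 359.9; 302.3; 253.9. Leavers over 10 years: 1,600 - 253.9 = 1,346.1.

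**4. Woman-years, as the mean of each year's start and end.** 1,440.0 + 1,158.4 + 948.7 + 791.7 + 665.0 + 558.6 + 469.2 + 394.2 + 331.1 + 278.1 = about 7,035.

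**5. Excess = leavers x days / 365.25.**

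| Period | 23 days | 36 days | Share of woman-years |
|---|---|---|---|
| Year 1 (320 leavers, 1,440 WY) | 20.2 WY | 31.5 WY | 1.4-2.2% |
| Years 1-10 (1,346 leavers, 7,035 WY) | 84.8 WY | 132.7 WY | 1.2-1.9% |

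A rate of 0.280 would read 0.280 x 1,440 / (1,440 + 20.2) = 0.276, or 0.274 with 31.5, in year 1. Over 10 years it would read 0.277 or 0.275.

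**6. Sensitivity to attrition.** The annual rates imply 1 - 0.80 x 0.81 x 0.83 x 0.84^7 = 84.1% cumulative discontinuation, not the stated 76%. That mismatch is a separate matter. With 76% (1,216 leavers; years 4-10 at a constant 10.9%; about 7,686 woman-years) the excess is 76.6-119.9 woman-years, or 1.0-1.6%.

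**7. Cross-check by simulation.** A Kaplan-Meier curve for 3,000,000 women at 0.28 per 100 woman-years compared censoring at removal with removal plus 30 or 43 days. The 10-year cumulative rate fell from about 2.75% to 2.71% or 2.69%, a relative 1.5-2.1%; year 1 fell by 1.7-2.4%. These exceed step 5 because no events were allowed in the 7-day window.

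**8. Undated loss.** The documents give neither the share undated nor the gap, so this is an illustration. Take the 5.8% cumulative expulsion by 60 months cited in Protocol 7.1.3, and assume that 10-50% of expulsions are undated with 46-134 days over-credited. Then 1,600 x 0.058 = 92.8 expulsions. The excess runs from 92.8 x 0.10 x 46 / 365.25 = 1.2 to 92.8 x 0.50 x 134 / 365.25 = 17.0 woman-years. On 5,004 woman-years over 5 years that is 0.02-0.34%, before the diary cap. It overstates the problem, because it includes time before the loss was noticed.

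**The case against.** **The follow-up test may not be meant as the last assessment.** The SAP never says that it is. Moreover, 10.2.2 read alone makes any confirmed pregnancy a failure, with no 7-day limit; that limit comes from 9.1 and 9.3. If the on-treatment scope limits events, it could be said to limit assessments too. But no text does so. Protocol 7.4, headed Pregnancy Assessment, covers positive tests through the 30-Day Safety Follow-up, and SAP 3 identifies pregnancies through that visit. A programmer following 10.2.2 would use that date.

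**The effect is immaterial.** At 0.28 per 100, 70.35 hundred woman-years give about 20 expected pregnancies, a Poisson relative standard error of about 22%. The bias is under a tenth of that, and the output is secondary and descriptive. This stands, and it is why the point is minor.

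**Stronger readings that a reader might infer.**
- *Every woman contributes the extra days.* That would give 1,600 x 23 or 36 / 365.25 = 101-158 woman-years. The documents do not support it: Protocol 6.7 has exemptions, Protocol 7.18.4 provides for missed visits, and removal at Month 121 puts completers' extra days after year 10.
- *All life tables, or the Pearl Index generally, are affected.* SAP 5.4 and 9.3 rule this out for known removal dates and for cycle-adjusted tables.
- *All time after an undated loss is spurious.* It is not: pregnancies after unrecognized expulsion count, so time before recognition is properly at risk. After a suspected loss, Protocol 6.3.2 asks for abstinence or non-hormonal contraception. Diary-reported use of another method excludes the cycle, and a final cycle under 23 days is dropped.

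**Conclusion.** The point holds, as a minor one. In life tables without cycle exclusions, the stated censoring rule credits device-free time in which no on-treatment event can occur, and it always favours the device. The size is at most 1.2-1.9% of woman-years over 10 years and 1.4-2.2% in year 1. This assumes the stated annual discontinuation rates, exits spread evenly within each year, removal at the discontinuation visit, and a follow-up test for every leaver. The last assumption makes it an upper bound in general. A late-reported expulsion with a known date can have a longer gap, since Protocol 6.7 lets the two visits coincide: "If the subject contacts the office with an expulsion that was 30 or more days ago, this visit may be combined". Such cases should be few.

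The undated-loss rule is a separate and smaller defect. Only time after the loss was reported is wrongly credited, and the diary count limits it. The documents do not allow it to be sized.

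Neither rule would change the efficacy conclusion. The reported yearly and cumulative pregnancy rates would be slightly low.

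**What to change.** 1. **SAP 10.2.2:** censor women without an on-treatment pregnancy at the earlier of the last pregnancy assessment and IUS discontinuation plus 7 days. This also settles the woman who conceives after that window: she is neither an on-treatment event nor a subject who did not get pregnant, so she has no censoring date now.
2. **SAP 5.4:** for an undated loss, do not let the last-use date run past the day before the contact at which the IUS was reported gone; delete the later-of-two clause. Time back to the actual loss stays in, consistent with counting pregnancies after unrecognized expulsion.
3. **SAP 5.3.5:** reconcile its last-clinic-visit rule with 5.4, so that a missing expulsion or removal date has one rule.

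The cost is a few SAP sentences and the matching program lines. No new data are needed.
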